11.2.1. Device Deficiencies

A device deficiency (DD) is an inadequacy of a medical device with respect to its identity, quality, durability, reliability, safety or performance. Device deficiencies include malfunctions, misuse or use errors, and inadequate labeling. All device deficiencies must be documented and submitted to Medtronic on the Device Deficiency eCRF. In addition, the Investigator must also determine and document on the eCRF device deficiencies that did not lead to adverse event but could have led to a serious adverse device effect:

- if either suitable action had not been taken,
- if intervention had not been made, or
- if circumstances had been less fortunate

11.2.2. Deaths

All subject deaths must be reported to Medtronic and the IRB/EC as soon as possible, but no more than 5 working days after learning of a subject's death, regardless of whether or not the death is related to the device system or therapy. If limited information is known, the Adverse Event eCRF must be completed with available information as soon as possible. As information becomes available, the eCRF will be updated. If the death occurs at a location remote from the study site, it is the study site's responsibility to make every attempt to retrieve all pertinent information related to the subject's death and submit the investigator's death summary of the known events surrounding the death to Medtronic or its designee. The Investigator should also attempt to determine, as conclusively as possible, whether such deaths are related to the device system, therapy, and/or procedure. If the death is evaluated as device, therapy and/or procedure related and unanticipated, the event will be reported as a USADE by Medtronic or its designee to the appropriate regulatory agencies. In addition, the principal investigator should follow commercial medical device reporting requirements. The principal investigator should provide as much of the following supporting documentation as possible for deaths:

- Death certificate
- Death summary/hospital records, if allowed by state/local law
- Autopsy report, if allowed by state/local law

All device system components that were being used at the time of the death should be returned to Medtronic for analysis, if applicable. Any subject death will be reported on the Adverse Event and Study Exit CRFs.

12. Data Review Committees

This study will not use a Clinical Events Committee or Data Monitoring Committee. Instead, all reported adverse events and device deficiencies will be reviewed by a Medtronic Medical Advisor to ensure consistent reporting as defined in Section 11.2.

13. Statistical Design and Methods

13.1 General Statistical Considerations

This study is a three-arm parallel design to explore effectiveness, and quality of life under three amplitude settings. For the primary objective, the primary analysis will be performed in the complete case (CC) population, or the population of subjects who have data available at baseline and follow-up based on their randomization. [REDACTED]

[REDACTED] Details of the primary and supporting analyses are outlined in the sections below.

Continuous measures will be reported as N, means, medians, standard deviations, minimums and maximums. All summaries will be provided by group. Categorical measures will be reported in frequency distributions.

Data analysis will be performed by Medtronic-employed statisticians or designees. A validated statistical software package (e.g., SAS version 9.2 or higher) will be used to analyze the study results.

The Statistical Analysis Plan (SAP) will be developed prior to data analysis and will include a comprehensive description of the statistical methods and reports to be included in the final study report. Any change to the data analysis methods described in the CIP will require an amendment only if it changes a principal feature of the CIP. Any other change to the data analysis methods described in the CIP, and the justification for making the change, will be described in the clinical study report.

13.1.1 Study Sample Size Justification

This study will explore the effect of three different amplitude settings (50% of sensory threshold, 80% of sensory threshold, and sensory threshold) on UUI episodes per day. Change of average UUI per day at 12-week follow-up will be assessed under each amplitude setting. This study requires approximately 42 implanted and randomized subjects with 12-week follow-up data to be analyzed for the primary objective. Assuming 10% attrition after full system implant and 80% therapy evaluation success rate, approximately 48 subjects will be implanted and randomized in 3 arms. However, these numbers may be exceeded to ensure that a minimum of 42 subjects complete the study.

The objectives are descriptive in nature. Confidence intervals will be calculated to describe the precision of the treatment effect in each arm. Precision is defined as one-half of the confidence interval (also known as the distance from the confidence limits to the mean). Sample size calculations were completed using the PASS 11 Confidence Intervals for One Mean module.

From the randomized portion of the InSite study¹³, a mean reduction of 2.1 ± 1.8 UUI episodes per day was observed at 3 months in SNM subjects; and from the all implanted cohort of InSite, a mean reduction of 2.3 ± 2.7 UUI episodes per day was observed at 3 months in SNM subjects. Based on this, we are assuming mean reductions between 1.8 and 2.3 will be observed in the study, along with standard deviations ranging from 2.2 to 2.7.

Based on a confidence interval constructed with a t-statistic, a two-sided type-I error rate of 0.05, and using the largest standard deviation assumed (2.7), a sample size of 14 subjects per arm will have a precision of 1.56 (Table 13-1). This precision is less than our lowest assumed treatment effect (1.8 UUI), so that it is expected that the lower 95% CI will be greater than 0 for all treatment arms, even in the scenario when the largest assumed standard deviation is applied.

Table 13-1. Standard deviations and precision

Standard deviation	Precision
2.2	1.27
2.3	1.33
2.4	1.39
2.5	1.44
2.6	1.5
2.7	1.56

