Assuming a mean reduction between 1.8 to 2.3 UUI episodes per day with a standard deviation of 2.2 to 2.7 UUI episodes per day is observed, with $\alpha=0.05$ two-sided and using a t-statistic to construct the confidence interval, a sample size of 14 subjects would have a precision of 1.56 UUI episodes per day for the assumption with a standard deviation of 2.7. Precision is defined as one-half of the confidence interval (also known as the distance from the confidence limits to the mean). This precision is less than our lowest assumed treatment effect (1.8 UUI), so it is expected that the lower 95% CI will be greater than 0 for all treatment arms, even in the scenario when the largest standard deviation was applied.

This sample size calculation intends to be sufficient to explore the effect of each of three amplitude settings on UUI; however, the sample size is not sufficient for between group comparisons.

4. Introduction

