5.1.3. Additional Measures

Additional measures include:

- Safety

█ [REDACTED]

█ [REDACTED]

6. Study Design

This is a prospective, multicenter, randomized, single-blind, feasibility study to explore the efficacy and quality of life of 3 different amplitude settings in patients with UUI. Subjects will remain blinded to their assigned randomization for the duration of the study.

Eligible subjects will sign a study-specific informed consent form (ICF). Following verification of eligibility criteria, subjects will go through therapy evaluation with the InterStim II System. After qualifying for the device implant, the subject will proceed with a neurostimulator device implant and randomization procedures. Subjects will be randomized to one of the three amplitude settings: 50% of sensory threshold, 80% of sensory threshold and sensory threshold.

Study requirements, including voiding diaries, quality of life questionnaires [REDACTED], and safety assessments will be completed as required in Figure 9-1: **Study Visits**. The study is expected to last approximately 16 weeks per subject following the enrollment visit. Subjects will be exited from the study after the 12-week follow-up visit is complete.

A minimum of forty-two implanted subjects (at least 14 subjects per arm) who have completed the 12-week follow-up visit are needed to assess the study primary objective. To account for screen failures, therapy evaluation conversion rate and loss to follow-up or missing data, it is anticipated that approximately 60 subjects will be consented and approximately 48 subjects will be implanted/randomized.

The study will be conducted at approximately 20 sites in the United States, Canada, and Europe.

This is an on-label, post-market study of an approved system. All subjects enrolled in the study will qualify under the approved indication for the InterStim II System.

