13.2.3 Endpoint success definition

This objective is to explore and characterize the reduction in number of UUI episodes under each amplitude setting from baseline. There are no pass/fail criteria proposed to define this endpoint success.

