## 7.2. General Methodology

### 7.2.1. General Statistical Considerations

Continuous measures will be reported as N, means, medians, standard deviations, minimums and maximums. All post-randomization data summaries will be provided by randomization group. Categorical measures will be reported in frequency distributions. No hypothesis testing will be performed.

For outcomes examining change from baseline, change ( $\Delta$ ) will be calculated as follow-up scores ( $S_v$ ) minus baseline scores ( $S_0$ ).

$$\Delta = S_v - S_0$$

Percent change will be calculated as 100 times the change divided by the baseline score.

$$\text{Percent change} = 100 * \Delta / S_0$$

Data analysis will be performed by Medtronic-employed statisticians or designees. A validated statistical software package (e.g., SAS version 9.4 or higher) will be used to analyze the study results.

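### Sample size: the lower 95% limit is said to be expected above 0 in all three arms, but under the plan's own assumptions the chance of this with 14 per arm is only 26% to 86%

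*Protocol*

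**What the plan says.** The same justification appears in the Protocol synopsis (Statistics), Protocol 13.1.1 and SAP 6. The planning values are worded as results to be seen in the trial. In Protocol 13.1.1 "we are assuming mean reductions between 1.8 and 2.3 will be observed in the study", with SDs of 2.2 to 2.7, and the synopsis supposes that a "standard deviation of 2.2 to 2.7 UUI episodes per day is observed". Precision is defined as the half-width of a two-sided 95% t interval for one mean. With 14 per arm and SD 2.7 it is 1.56 (Protocol Table 13-1, SAP Table 1).

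Because 1.56 is less than 1.8, the synopsis concludes that "it is expected that the lower 95% CI will be greater than 0 for all treatment arms". Protocol 13.1.1 draws the same conclusion and, like the other two places, extends it to the largest SD: "it is expected that the lower 95% CI will be greater than 0 for all treatment arms, even in the scenario when the largest" of the assumed SDs applies. No probability is attached to the statement.

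Protocol section 6 makes 14 per arm the planned minimum: "A minimum of forty-two implanted subjects (at least 14 subjects per arm". Two further statements limit what depends on the sentence. Protocol 13.2.3 says "There are no pass/fail criteria proposed to define this endpoint success", and SAP 7.2.1 says "No hypothesis testing will be performed".

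**The concern.** A half-width below the assumed mean shows only what happens when an arm lands exactly on the assumed mean and SD. Three arms of 14 will not do that. Each observed mean varies around its true value, each observed SD changes the width of its own interval, and the claim requires all three intervals to clear 0 together. If an arm's true mean were 1.8, it would observe less than 1.8 about half the time, and at SD 2.7 there is little room below that.

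This comparison is the only reason the documents give for regarding a precision of 1.56, and so 14 per arm, as adequate. A reader will take it that all three intervals should exclude 0. If one arm's interval then includes 0, that reader could take it as a sign that the amplitude setting does not work, when it would be an ordinary result under the plan's own assumptions.

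**Working it through.** **Inputs** (Protocol 13.1.1 and SAP 6): n = 14 per arm, three arms, two-sided 95% t interval, mean reduction 1.8 to 2.3, SD 2.2 to 2.7. The scale is reduction, so a lower limit above 0 corresponds to an upper limit below 0 on the follow-up-minus-baseline scale of SAP 7.2.1.

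**Step 1: reproduce the plan's figures.** Half-width = t(0.975, 13) × SD/√14, with t(0.975, 13) = 2.1604. For SD 2.2, 2.3, 2.4, 2.5, 2.6 and 2.7 this gives 1.270, 1.328, 1.386, 1.443, 1.501 and 1.559. Both tables are reproduced to rounding.

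**Step 2: the margin in the named scenario.** At SD 2.7 the standard error is 2.7/√14 = 0.722. The lower limit at an observed mean of 1.8 is 1.800 − 1.559 = 0.241. With the SD held at 2.7, a shortfall of 0.241 in the observed mean, or 0.241/0.722 = 0.33 of a standard error, brings the limit to 0.

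**Step 3: the probability that the limit exceeds 0.** Take the assumed values as true parameters, with normally distributed changes. The lower limit exceeds 0 when the one-sample t statistic exceeds 2.1604. That statistic follows a noncentral t distribution with 13 degrees of freedom and noncentrality mean × √14/SD. For three independent arms with the same mean and SD, the probability is cubed.

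| Mean, SD | Lower limit if observed exactly | Noncentrality | One arm | All three arms |
|---|---|---|---|---|
| 1.8, 2.7 | 0.24 | 2.494 | 63.6% | 25.7% |
| 1.8, 2.2 | 0.53 | 3.061 | 80.8% | 52.7% |
| 2.05, 2.45 (mid-range) | 0.64 | 3.131 | 82.5% | 56.1% |
| 2.3, 2.7 (cited all-implanted cohort) | 0.74 | 3.187 | 83.8% | 58.8% |
| 2.3, 2.2 | 1.03 | 3.912 | 95.0% | 85.9% |

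In the first row, at least one interval includes 0 with probability 1 − 0.257 = 0.743. Simulation of 300,000 three-arm trials per corner agrees: 63.7% and 25.8% at the first corner, 95.1% and 85.9% at the last.

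**Step 4: sensitivity to n.** If all of about 48 randomized subjects contribute, each arm has 48/3 = 16. The probabilities are then 70% per arm and 35% for all three at 1.8, 2.7, and 97% and 92% at 2.3, 2.2. This is an illustration and not an upper bound, since Protocol 13.1.1 says "these numbers may be exceeded to ensure that a minimum of 42 subjects complete the study".

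**Step 5: sensitivity to normality.** The documents give no distribution for the changes. I assumed shifted-gamma changes with skewness −1.5, 0 and +1.5 (n = 14, 400,000 samples per setting). At 1.8, 2.7 the results are 64% to 70% per arm and 26% to 35% for all three. At 2.3, 2.2 they are 89% to over 99% per arm and 70% to 99% for all three.

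**The case against.** The strongest reply is that the sentence is conditional and true on its condition: the planning values are stated as observed values, and 1.8 − 1.56 is positive. It is also true on average. With the assumed values as true parameters, the mean lower limit is 0.27, 0.55, 0.77 and 1.05 at the four corners (1.8, 2.7; 1.8, 2.2; 2.3, 2.7; 2.3, 2.2), and each single arm is more likely than not to clear 0. A precision-based, descriptive design needs no power. The half-width itself already reflects sampling variation in the mean. The synopsis also says that the calculation is meant to explore each setting and does not support comparisons between groups. Finally, the 26% needs all three arms at the lowest mean and the largest SD. Neither cited cohort has that pairing, and the randomized cohort (2.1 ± 1.8) would give 98% per arm and 94% for all three.

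Much of this stands: no figure in the tables is wrong, no power target is missing, and 26% is the least favourable corner. It does not rescue the sentence. The text speaks of all arms and names the largest SD as a case that is still covered, which is a joint forecast that an average per arm does not support. The SD of 1.8 lies outside the plan's own range of 2.2 to 2.7. At mid-range, and at the cited all-implanted values, all three limits clear 0 only a little more often than not.

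**Conclusion.** The concern holds, at minor severity. The precision figures are right, and the statement is true for an arm that observes exactly the assumed mean and SD. As a forecast for all three arms it is too confident: with 14 per arm the probability is 64% to 95% per arm and 26% to 86% jointly, and about one in four in the scenario that the text singles out.

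These figures assume normally distributed changes, independent arms, exactly 14 analysed per arm, and the same true mean and SD in each arm. Skewness moves them, but at the least favourable corner the joint probability stays at or below 35% over the range tried. The consequence is limited, because no test, success rule or decision depends on any limit exceeding 0.

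**What to change.** Keep the sample size and both precision tables. In the synopsis, Protocol 13.1.1 and SAP 6, replace the sentence about the expected lower limit with:

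> If an arm observes exactly the assumed mean and SD, its lower 95% limit for the mean reduction lies above 0 (0.24 in the least favourable case). If the assumed values are true, changes are normally distributed and arms are independent, the probability with 14 subjects per arm that the lower limit lies above 0 ranges from about 64% (mean 1.8, SD 2.7) to 95% (mean 2.3, SD 2.2) for one arm, and from about 26% to 86% for all three arms together.

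The cost is a wording change in three places and a less favourable stated property that rests on named assumptions. It needs no extra subjects, introduces no hypothesis test and changes no endpoint or analysis.

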13.1.2 Description of demographic and baseline variables

Summary statistics will be provided, by group, for baseline and demographic variables for subjects who are enrolled and randomized.

13.1.3 Center Pooling

Data from all study centers will be pooled for the analysis. There are no planned statistical methods to test for treatment differences among centers. The study will be conducted at approximately 20 centers in the United States, Canada and Europe.

13.1.4 Missing Data

Missing data imputations will not be performed.

13.1.5 Interim Analysis

No formal interim analysis is planned for this study. Interim descriptive summaries may be performed; however, if provided, the study team, investigators and site personnel will be blinded to this information. No study decisions will be made from descriptive summaries; therefore, no sample size adjustment is needed.

13.1.6 Reports

A final report will be generated for this study. Periodic progress reports may also be generated for the study.

13.1.7 Study Success

As the study objective is to characterize the efficacy and QoL of 3 different amplitude settings, there is no pass/fail criteria proposed to define study success.

13.1.8 Subgroup Analyses

Subgroup analyses will be detailed in the SAP, if any will be conducted.

13.1.9 Patient Populations

The full analysis patient set (FAS) includes all subjects who signed the study-specific ICF and enrolled in the study.

The complete case (CC) patient set will consist of the subject set who have data available at baseline and follow-up.

13.2 Primary Objective

13.2.1 Primary objective

To explore the effect of three different amplitude settings (50% of sensory threshold, 80% of sensory threshold, and sensory threshold) on urinary urge incontinence (UUI) episodes per day.

Descriptive statistics for change in UUI from baseline to 12 weeks will be provided in each randomized group.

Negative values for a change from baseline represent an improvement in UUI episodes and positive values represent an increase in UUI episodes.

13.2.2 Experimental design

Subjects' number of UUI episodes will be reported in the voiding diary. Data will be collected daily in the 3 days prior to each visit for all subjects and the value reported at each visit will be calculated as the daily average of the available diary days at that visit. All available data will be used for analysis, regardless of whether 1 day is available or 3 days are available. The change in scores from Baseline to 12 weeks will be calculated for each subject and the average change across all subjects in each group will be reported.

13.2.3 Endpoint success definition

This objective is to explore and characterize the reduction in number of UUI episodes under each amplitude setting from baseline. There are no pass/fail criteria proposed to define this endpoint success.

13.2.4 Analysis methods

Descriptive statistics including mean, standard deviation, 95% confidence intervals, median, minimum and maximum will be provided.

13.2.5 Analysis populations and sensitivity analyses

The analysis population for this objective will be on the CC population, as described in Section 13.1.9.

In addition to the primary analysis, an as-treated (AT) sensitivity analysis will be completed to assess the robustness of results. The AT analysis will include the population of subjects who have data available at baseline and 12 weeks, but will analyze subjects according to the treatment they receive.

In addition to the summaries described above, responder rate analyses will be conducted to further describe the treatment effect of each randomization group. Responder rates will be described as the percent of patients who achieve therapeutic success, defined as $\geq 50\%$ reduction in average UUI episodes/day from baseline to 12 weeks, divided by the number of subjects included in the analysis.

Responder rate analyses will be completed based on the CC and AT analyses described above.

13.3 Secondary Objective

13.3.1 Secondary objective

To explore the effect of three different amplitude settings (50% of sensory threshold, 80% of sensory threshold, and sensory threshold) on quality of life with the ICIQ-OABqol Questionnaire.

Descriptive statistics for the change in all domains of this questionnaire from baseline to 12 weeks will be provided in each randomized group.

13.3.2 Experimental design

The change in each subscale score from Baseline to 12 weeks will be calculated for each subject and the average change across all subjects in each group will be reported.

13.3.3 Endpoint success definition

This objective is to explore and characterize the QoL under each amplitude setting from baseline to 12 weeks. There are no pass/fail criteria proposed to define this endpoint success.

13.3.4 Analysis methods

Descriptive statistics including mean, standard deviation, 95% confidence intervals, median, minimum and maximum will be provided.

13.3.5 Analysis populations and sensitivity analyses

The analysis population for this objective will be on the CC population, as described in Section 13.1.9.

In addition to the primary analysis of the secondary objective, an as-treated (AT) sensitivity analysis will be completed to assess the robustness of results. The AT analysis will include the population of subjects who have data available at baseline and 12 weeks, but will analyze subjects according to the treatment they receive.

13.4 Additional Measures

Additional measures have been added to provide relevant information on parameters of interest in SNM therapy under different amplitude settings and to provide additional information.

Additional measures to summarize are:

- Incidence of device-related, procedure-related and/or therapy-related adverse events

█ [REDACTED]

█ [REDACTED]

Reportable device-related, procedure-related and/or therapy-related adverse events will be summarized for subjects who are implanted and randomized under each amplitude setting. Device-deficiencies will be summarized in the similar fashion. In addition, serious adverse events will be summarized.

█ [REDACTED]

█ [REDACTED]

█ [REDACTED]

14. Ethics

14.1.Statement(s) of Compliance

The study will be conducted in accordance with this protocol, the ethical principles that have their origin in the Declaration of Helsinki have been implemented in this clinical study by means of the informed consent process, EC/IRB approval, study training, and risk benefit assessment. In addition, all applicable laws and regulatory requirements of the country/ies in which the study is conducted will be followed and in accordance with GCP.

- In the US, the study will be conducted in accordance with 21 CFR§11 Electronic Records, Electronic Signatures, 21CFR§50 Protection of Human Subjects, 21CFR§56 IRB, and 21CFR§803 Medical Device Reporting. Financial disclosures will be collected; however, this study is not considered a “covered study” under 21 CFR§54 Financial Disclosure by Clinical Investigators.
- In Europe, the study will be conducted in accordance with regional or national regulations, as appropriate.
- In Canada, the study will be conducted in accordance with Canada Medical Devices Regulations, 1998 (SOR/98-282), and the Guidance document for Mandatory Problem Reporting.

Any additional requirements imposed by the IRB/EC or governing regulatory authority shall be followed, if appropriate.

Medtronic will distribute the approved version of the CIP and all other materials required to conduct the study. Prior to site activation, Medtronic will provide study training relevant and pertinent to the involvement of personnel conducting study activities and investigator responsibilities. Medtronic will not activate any site until the required approval/favorable opinion from the Institutional Review Board (IRB)/Ethics Committee (EC) or notification/approval from a regulatory authority have been obtained, if appropriate.

Site personnel must inform Medtronic of any change in status of the IRB/EC approval once the site has started enrollment.

